1.1. Background

The current shift from paternalistic to participatory models of care emphasizes the role of patients and their environment in healthcare decision-making. Effective communication is vital for achieving treatment goals, but various factors can impede patients' comprehension and retention of information, essential for treatment adherence. During clinical-patient communication, especially in post-check-up or discharge instructions, healthcare professionals often convey complex information briefly, overwhelming patients. Studies reveal that 40-80% of information is immediately forgotten, with up to 50% remembered inaccurately. This not only jeopardizes treatment adherence but also exposes patients to risky behaviors. Older adults tend to forget a significant percentage (40-80%) of information provided by healthcare personnel. Addressing communication challenges is crucial to enhancing patient understanding and, consequently, treatment outcomes.

1.2. Objectives

1.2.1. General objective

Develop and evaluate an automatic association system of medical instructions to pictograms to positively impact the understanding, retention, and adherence to treatment for patients diagnosed with bronchial asthma receiving care at primary health centers.

1.2.2. Specific Objectives

- Develop the SIMAP system to automatically complement medical instructions with pictograms in the context of managing and treating bronchial asthma, ensuring interoperability with existing EHRs
- Validate the impact of SIMAP on understanding, retention, and therapeutic adherence among patients consulting at an Asthma respiratory Units (ARU) through a randomized clinical trial.

2. Research Methodology for Clinical Validation

2.1 Clinical Trial Description

In order to determine the effects of implementing a pictogram platform to facilitate understanding and therapeutic adherence, a randomized parallel-group, triple-masked clinical trial will be conducted with patients recently diagnosed with asthma (≤ 15 days) who enter the Asthma respiratory Units (ARU), hereinafter referred to as ARU, at the Family Health Centers (CESFAM) belonging to the Municipal Health Corporations of the cities of Valparaíso, San Antonio, Hualpén, and Talcahuano. This protocol has been drafted in accordance with the 2010 CONSORT statement (CONSORT 2010).

2.2 Participants

2.2.1 Verification of Inclusion and Exclusion Criteria

All participants in this study will be patients who enter the Asthma respiratory Units (ARU) of the CESFAM belonging to the Municipal Corporation of Valparaíso, Municipality of San Antonio, Municipal Corporation of Hualpén, and Health Administration Directorate of the Municipality of Talcahuano. The selection criteria for study participants are:

Inclusion Criteria

- Adult patients aged 18 to 65 years with a recent diagnosis of bronchial asthma (<=15 days) based on the 2018 criteria from the Global Initiative for Asthma (GINA) (Reddel et al., 2015), recommended by the Ministry of Health of Chile.
- Clinically substantiated diagnosis with spirometry results compatible with the guidelines of GINA.
- Patients initiating bronchodilator treatment, including at least one inhaled corticosteroid and a short-acting bronchodilator.

Exclusion Criteria

- Patients with obstructive bronchial pathology other than bronchial asthma (chronic obstructive pulmonary disease, mixed states, etc.).
- Patients who participated in the design phase of the pictograms (Stage 1 of the project).
- Patients with a diagnosis of dementia, harmful alcohol consumption, and other drug-related diagnoses according to the International Classification of Diseases (ICD-10),
- Patients with significant ophthalmological pathology that hinders the use of pictograms,
- Patients who do not wish to participate in the project.

2.3 Clinical Intervention

2.3.1 Recruitment

A healthcare professional designated by the Director of the CESFAM will be responsible for reviewing the selection criteria for patients entering the ARU during the recruitment period. Upon the first visit (patient's entry into the ARU), if the patient meets the selection criteria, the professional designated by the CESFAM director will introduce the project to the patient and inquire if they would like to meet with the researchers for an invitation to participate in the project by signing the informed consent form. If the patient agrees, the healthcare professional designated by the CESFAM director will inform the project director or a team member designated by her.

Following this, the clinical professional (recruiter) hired by the project will formally invite the patient to participate through the reading and signing of the informed consent. After signing the informed consent, the clinical professional employed by the project (recruiter) will proceed to conduct an interview with the participating patient to obtain a bio-sociodemographic profile, including demographic variables such as gender and age, nationality, time with asthma symptoms, educational level (categorized as basic, middle, higher, and postgraduate education), number of drugs in use, morbidity history as established by the Charlson Comorbidity Index,

smoking history with the corresponding pack-years index, and drugs in use. The initial interview will be conducted by a clinical professional employed by the project. Once the profile is completed, the same clinical professional employed by the project will record the level of disease control at the beginning of the study (time of patient participation acceptance - T0), based on the Asthma Control Test (ACT) questionnaire. This questionnaire has been selected based on its diagnostic capabilities, validation in the Spanish language, and widespread use in both traditional clinical practice and asthma research in Chile. It is currently recommended in national clinical guidelines to establish the level of disease control (Schatz et al., 2006; Vega et al., 2007). ACT scores are established based on 5 questions on a 5-point Likert scale, where higher scores indicate better disease control. Patients with scores above 19 points are considered to have well-controlled asthma.

2.3.2 Assignment to intervention group A or control group B

- Patients will be randomized using a permuted block method to receive one of two possible intervention strategies A or B.
- The permuted block technique aims to ensure a periodic balance in the number of subjects assigned to each intervention or control group (Molina et al., 2015).
- The random assignment sequence will be generated by technical staff of the project with the support of a statistician.

Intervention Group A: This intervention involves utilizing a pictogram system named SIMAP (Automatic Association System of Medical Instructions to Pictograms), which was developed during the initial phase of the study. In essence, SIMAP comprises a series of pictograms intended to enhance the understanding of medical instructions provided by the healthcare team regarding asthma management. The pictograms will be designed by a panel of experts, as detailed in the previous sections of the project, and validated among adult patients consulting in the same population where this study will be implemented. The designed pictograms are specifically tailored to certain elements within the management of bronchial asthma.

This intervention entails furnishing the patient with the instruction sheet given by the clinical staff of the CESFAM as part of their care, but supplemented with pictograms (automatically generated by SIMAP). The provided instructions include images supporting guidance for recognizing bronchodilators, indicating their method of use (daily dose, usage schedule, or as needed), specifications of bronchodilator families with their functions (disease-controlling and symptom-relieving drugs), inhalation technique of bronchodilators, and the use of an inhalation chamber in the process.

The pictograms will be administered by the clinical professional of the CESFAM designated by the Director or by the clinical professional hired by the project (recruiter). This depends on the care process of the CESFAM participating in this study and the availability of hours of the clinical professional of the CESFAM designated by the Director to support the project.

Control Group B: This corresponds to those patients selected and who agreed to participate in the study but will not be assigned to receive the SIMAP system (control group) through the randomization method. These patients will receive their medical instructions in the usual manner, as established by the healthcare team of the participating clinics. Additionally, these patients will receive an informative brochure on bronchial asthma, provided as part of the

standard education when explaining the disease. These brochures will be crafted using everyday language in Spanish, without incorporating pictograms into their content.

The research team will not intervene in any way in the selection of bronchodilators by the healthcare team or in any other decision-making regarding the management of bronchial asthma among participating patients.

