2.3.3 Training for those providing interventions A and B

The clinical and technical team of the SIMAP project will train the clinicians working in the participating ARUs of the project in the clinical trial and use of SIMAP. Two training sessions of 30 minutes each, delivered in groups, are planned. In the first of these sessions, an explanation will be provided about the intervention, as well as essential principles regarding how pictograms would facilitate users' understanding of the instructions. The second session will involve the direct application of these pictograms to simulated patients under the guidance of the SIMAP design team.

2.3.4 Follow-up (procedure developed in the same way for both Group A and B)

The follow-up will be conducted according to what is shown in Table I.

Table I: Follow up procedure beginning (t0), 7 days (t1), 30 days (t2) and 60 days (t3)

		Study Period						
		CESFAM Professional	Clinical professional hired by the project (recruiter)	Clinical professional hired by the project (follow-up)	t0	t1	t2	t3
Recruitment	Application of Eligibility Criteria	X			X			
	Informed Consent Signature		X		X			
	Bio-sociodemographic Profile		X		X			
	Charlson Index		X		X			
	ACT test		X		X			
Intervention A	Delivery of instructions with Pictograms	X	X		X			
Intervention B	Delivery of informative brochure		X		X			
Follow-up	ACT test			X		X	X	X
	Inhalation			X		X	X	X

	Technique Adherence Guideline							
--	-------------------------------------	--	--	--	--	--	--	--

3. Data & Statistical Analysis Plan

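### The role that hands over the allocated material is not held constant between arms, so an effect of the deliverer cannot be separated from the pictogram effect

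*Combined protocol and SAP*

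**What the plan says.** **Arm A.** Section 2.3.2 states: "The pictograms will be administered by the clinical professional of the CESFAM designated by the Director or by the clinical professional hired by the project". It adds: "This depends on the care process of the CESFAM participating in this study and the availability of hours of the clinical professional of the CESFAM". In Table I (section 2.3.4) the row "Delivery of instructions with Pictograms" is marked under both the CESFAM professional and the recruiter, at t0. The underlying sheet comes from the clinic: "This intervention entails furnishing the patient with the instruction sheet given by the clinical staff of the CESFAM as part of their care".

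**Arm B.** Under Control Group B, section 2.3.2 states: "These patients will receive their medical instructions in the usual manner, as established by the healthcare team of the participating clinics". These instructions have no row in Table I. A brochure is given in addition, described as part of the "standard education when explaining the disease", with no deliverer named. In Table I the row "Delivery of informative brochure" is marked under the recruiter only, at t0.

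**Training and analysis.** Section 2.3.3 describes SIMAP training for ARU clinicians and does not mention the recruiter. Section 3.4 foresees model adjustment if group characteristics are imbalanced; it names neither deliverer nor centre. No section provides for recording who delivered the material.

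**The concern.** Table I shows delivery at t0 and none later, so the intervention rests on that handover. The outcomes are ACT score and inhalation technique, and it is plausible that both respond to who hands over and explains the material. The deliverer is settled after allocation and under a different rule in each arm, so randomisation does not balance it. If the deliverer matters, the A minus B contrast contains that effect as well as the pictogram effect, in whichever direction it acts. Adjusting for centre would not remove it, because the difference lies between arms inside a centre. The second specific objective is to validate the impact of SIMAP, so a difference that might come from staffing would not answer the question cleanly.

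**Working it through.** **1. The two permitted routes side by side**

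| Item | Arm A sheet delivered by CESFAM professional | Arm A sheet delivered by recruiter |
|---|---|---|
| Arm A: sheet with pictograms | clinic staff | project staff |
| Arm B: brochure (Table I) | project staff | project staff |
| Arm B: usual instructions (section 2.3.2) | clinic staff | clinic staff |
| Allocated material, A against B | different role | same role |
| Instructions, A against B | same role | sheet from project staff in A, instructions from clinic staff in B |

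Each route matches one comparison and leaves the other unmatched. The plan gives no share of arm A for either route.

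**2. Size if a deliverer effect exists (illustration)**

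The plan gives no effect size, SD or deliverer share, so it has no figure of its own to reproduce here. Inputs:
- Total of 48 patients (section 3.2); 24 per arm assumes 1:1 allocation and no loss.
- g, the deliverer effect in SD units: assumed 0.2, 0.3 or 0.5.
- q, the share of arm A whose allocated material comes from a different role than in arm B: assumed 0.5 or 1.
- No true SIMAP effect; unadjusted two-sided 5% t-test.

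Formulas:
- Standard error of the mean difference = √(2/24) = 0.289 SD.
- Bias = q × g.
- Rejection probability from the noncentral t with 46 degrees of freedom and noncentrality (q × g)/0.289.

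| g (SD) | q | Bias (SD) | Noncentrality | False-positive rate |
|---|---|---|---|---|
| any | 0 | 0 | 0 | 5.0% |
| 0.2 | 0.5 | 0.10 | 0.35 | 6.3% |
| 0.2 | 1 | 0.20 | 0.69 | 10.4% |
| 0.3 | 0.5 | 0.15 | 0.52 | 8.0% |
| 0.3 | 1 | 0.30 | 1.04 | 17.4% |
| 0.5 | 0.5 | 0.25 | 0.87 | 13.6% |
| 0.5 | 1 | 0.50 | 1.73 | 39.6% |

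A normal approximation gives close values: 6.4% and 10.7% for g = 0.2, and 13.9% and 41.0% for g = 0.5.

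The model covers only the allocated material (sheet in A, brochure in B) and gives every mismatch the same sign. It does not cover the instruction mismatch in the last row of the first table. If the two routes push in opposite directions, they could partly cancel.

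**3. Could the analysis repair it?**

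Not well. On Table I's reading, the deliverer of the brochure does not vary in arm B, so a deliverer effect cannot be estimated there. In arm A it would rest on about 24 patients whose deliverer was not randomised.

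**The case against.** The strongest reply is that the sheet in A and the brochure in B are unlike items. The counterpart of A's sheet is B's usual instructions, and where the CESFAM professional delivers A, clinic staff give those in both arms. The recruiter also sees every patient at t0 for consent, profile, Charlson index and ACT, so contact with project staff is partly balanced. Fitting delivery to each centre's process is a reasonable pragmatic choice when a system is compared with usual care.

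Much of this stands. It shows that the mismatch depends on the route and may be small. It does not show that the deliverer is constant: the recruiter route opens the instruction mismatch, and the flexibility exists in arm A only. A pragmatic design can vary staffing between centres without varying it between arms.

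Two stronger readings are tempting and should not be adopted:
- A reader might infer that the text on arm B contradicts Table I about the brochure. It does not. Calling the brochure part of standard education names no deliverer, so both statements can be true. This is an ambiguity.
- A reader might infer that having the recruiter deliver in both arms settles the matter. On its own it does not, because arm B's instructions would still come from the clinic team while project staff give out A's instruction sheet.

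**Conclusion.** The concern holds in a limited form. The plan allows the role that delivers the allocated material to differ by arm within a centre, and nothing in the design or analysis separates an effect of that role from the effect of the pictograms. A reader might go further and conclude that the SIMAP effect is in fact mixed with a deliverer effect. The documents do not support that, because they give neither the share of patients on each route nor any evidence that the deliverer changes the outcome. It is a risk of unknown size and direction.

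The false-positive rates of 6.3% to 39.6% show what would follow from deliverer effects of 0.2 to 0.5 SD affecting half or all of arm A. They depend on those assumptions, on 1:1 allocation and on mismatches of one sign; they do not estimate a bias in this trial. The point is worth acting on because the remedy is cheap beforehand and weak afterwards.

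**What to change.** Reconcile section 2.3.2 (both arms) with Table I and state one rule:
- In both arms the clinic team gives its usual care instructions.
- Within each centre the allocated material (pictogram-supplemented sheet in A, brochure in B) is handed over by the same role, in the same t0 contact. The recruiter is one option, already permitted in both arms. A centre that uses its CESFAM professional for A uses that role for B too.

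Then:
- mark matching columns for A and B in Table I and add a row for the usual instructions in both arms;
- include whichever role delivers in the training of section 2.3.3;
- record the deliverer's role for each patient.

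Clinical care and drug choice stay with the clinic team, as section 2.3.2 already provides.

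The cost is a wording change, one form field and, where the recruiter delivers, a place in the two planned 30-minute training sessions if the recruiter is not already included. No patients or visits are added. Centres lose some flexibility in staffing arm A delivery, and recruiter delivery is slightly less like routine use of SIMAP.

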3.2. Sample Size

In this stage, we will be working with new patients entering the ARU. Based on the actual population size of adult patients with bronchial asthma recorded from 2019 to 2021 in the participating centers of the project, we have considered a minimum sample size of 48 patients, with a 10% margin of error and a 95% confidence level. We anticipate recruiting this sample within a period of no more than 6 months from the entry of the first patient. The sample calculation takes into account the years during which the COVID-19 social and health crisis occurred. Additionally, due to the lack of previous literature on the evaluation of pictograms for asthma control, it is not feasible to calculate a sample size based on the effect size to be achieved. Ideally, we aim for a homogeneous sample according to the a priori population of entries for each participating center. However, in case of recruitment difficulties at any health center, the sample will be obtained based on the center with the highest availability of patient entries that meet the selection criteria. Considering the measurement of the primary and co-primary outcomes, we plan to randomize a minimum of 48 patients for Stage 2 of the clinical validation of SIMAP.

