3.4. Analysis Strategy

The statistician hired by the project will conduct the data analysis for Stage 2 of the study. Descriptive analysis will initially involve means, standard deviation, absolute and relative frequencies. For inferential analysis, either Student's t-tests or Mann-Whitney tests will be employed to compare means based on the distribution and variances of the obtained data. The Fisher's Exact Test will be used for evaluating qualitative variables.

The primary outcome will be assessed concerning the difference in mean scores observed in bronchial asthma control questionnaires (ACT) between groups at each time point through a profile analysis. The secondary outcome will be evaluated based on the proportion of patients adhering to recommendations regarding the correct use of bronchodilators between both groups. Any intra-group comparisons of qualitative data will be conducted using the ANCOVA or Kruskal-Wallis statistic, depending on the distribution of quantitative data.

All analyses will be carried out by a statistician unaware of the treatment assignment of the participants. Outcomes will be analyzed on an intention-to-treat basis (intervention or control group). In the event of an imbalance in the characteristics of the groups established by the randomization process, potential adjustments to the models will be made. Any model generated will consider the presence of potential interactions between independent variables during its design. Maximum likelihood principles will be ensured based on residual analysis.

To preserve the intention-to-treat principles, missing data will be handled using multiple imputation techniques. All analyses will be performed by a masked statistician using R Project software.

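### No stratification by municipality and no centre term are specified, so with 48 patients chance imbalance within a municipality is common and any between-municipality variation stays in the error term

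*Combined protocol and SAP*

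**What the plan says.** Section 2.1 recruits from "Family Health Centers (CESFAM) belonging to the Municipal Health Corporations of the cities of" Valparaíso, San Antonio, Hualpén and Talcahuano. The number of individual centres (CESFAM) is not given.

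On allocation, section 2.3.2 states: "Patients will be randomized using a permuted block method to receive one of two possible intervention strategies A or B". It gives no block size, allocation ratio, number of lists or stratification factor. On who hands over the pictograms (a CESFAM professional or the project's recruiter), the same section says: "This depends on the care process of the CESFAM participating in this study and the availability of hours". The description of the control group leaves the usual instructions, and all drug choices, to the local healthcare teams.

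Section 3.2 sets the size: "we plan to randomize a minimum of 48 patients for Stage 2 of the clinical validation of SIMAP". It aims for a spread that follows each centre's expected entries. If a centre recruits poorly, however, "the sample will be obtained based on the center with the highest availability of patient entries that meet the selection criteria".

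Section 3.4 names t-tests or Mann-Whitney tests, Fisher's exact test and a profile analysis of ACT. None of these is said to include centre. The nearest provision is: "In the event of an imbalance in the characteristics of the groups established by the randomization process, potential adjustments to the models will be made". It names no covariate and no trigger.

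**The concern.** Local conditions may affect both the outcome and the way the intervention reaches the patient. The plan itself makes arm A delivery depend on the centre and lets the spread of patients over centres drift. The usual response is to balance the arms within municipality and to carry municipality into the analysis.

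Without that, two things are at stake in a trial of 48. In the one trial that is run, the arms may differ clearly in their municipality mix, which makes the result harder to defend. And whatever ACT variance lies between municipalities adds to the noise around the treatment difference, in a trial with no power calculation and little precision to spare.

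**Working it through.** **Inputs from the documents.** 48 patients, four municipalities, individual randomisation in permuted blocks, no centre term.

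**Assumptions not in the documents.** 1:1 allocation (24 per arm); blocks of 4 unless stated; municipality sizes of 12/12/12/12 or 24/12/8/4; a between-municipality share of ACT variance (call it r) of 0 to 0.20; a true effect of 0.83 SD, chosen because it gives about 80% power with 24 per arm.

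**1. The plan's own figure.** Section 3.2 derives 48 from a 10% margin of error at 95% confidence. The formula 1.96² × 0.5 × 0.5 / 0.10² gives 96.04. With a finite population correction, 96.04 / (1 + 95.04/N) gives 47.75, hence 48, at N = 94. N is not stated, so the figure is attainable but cannot be verified. It says nothing about power.

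**2. Chance imbalance.** If patients arrive in random order of municipality and 24 of the 48 get A, the counts of A per municipality are multivariate hypergeometric, whatever the block size. There are C(48,24) = 32,247,603,683,100 allocations. For four municipalities of 12, those with every split 7:5 or closer number
924⁴ + 12 × 924² × 792² + 6 × 792⁴ = 9,516,209,598,720,
where 924 = C(12,6) and 792 = C(12,5). Their share is 0.295, so:
- at least one municipality splits 8:4 or worse: 1 - 0.295 = 70.5% (simulation: about 71%);
- at least one splits 9:3 or worse, by the same count: 28.8% (simulation: about 29%).

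With sizes 24/12/8/4, at least one municipality reaches 75:25 or worse in about 72% of trials, and at least one has all its patients in one arm in about 11%.

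**3. Bias and type I error.** In simulation the mean difference between arms in each municipality's share was 0 within Monte Carlo error. The unadjusted test rejected a true null in 4.6% to 5.2% of trials for r from 0 to 0.20.

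**4. Size of the chance shift.** For a municipality of 12, the number in A has variance 12 × ¼ × 36/47 = 2.30, so SD 1.52. The difference between arms in that municipality's share, (2k - 12)/24, then has SD 1.52/12 = 0.126. Over four municipalities the shift in the ACT difference has SD √(r × 4 × 0.126²):
- r = 0.10: 0.080 SD units;
- r = 0.20: 0.113 SD units.

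The standard error of the whole comparison is √(2/24) = 0.289.

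**5. Power.** For stratified blocks with municipality in the model, noncentrality is 0.83 / √((1 - r) × 2/24) on 48 - 5 = 43 degrees of freedom. The column without stratification or a municipality term comes from 20,000 simulated trials per row (municipality effects normal with variance r, residual variance 1 - r, equal sizes, blocks of 4).

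| r | Noncentrality | Stratified and adjusted | Unstratified, unadjusted | Change |
|---|---|---|---|---|
| 0 | 2.88 | 80.2% | 80.0% | about 0 |
| 0.05 | 2.95 | 82.2% | 80.3% | about +2 |
| 0.10 | 3.03 | 84.2% | 81.4% | about +3 |
| 0.20 | 3.21 | 88.1% | 82.3% | about +6 |

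Simulating both designs, with sizes 24/12/8/4 and with mixed blocks of 2, 4 and 6 as well, the change ranged from 0 to -1 point at r = 0, 0 to +3 at 0.05 to 0.10, and +4 to +6 at 0.20. A smaller run of 4,000 trials gave +4 at r = 0.10. The Monte Carlo error of such a difference is about √(2 × 0.8 × 0.2 / 4,000) = 0.9 points, so this is consistent.

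**6. Adjusting without stratifying.** After unstratified blocks, a municipality term loses about 6% of the information on average. At r = 0, noncentrality falls to 2.88 × √0.94 = 2.79 and power to about 77%, against about 80% when the blocks are stratified.

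**The case against.** The strongest reply is that nothing here invalidates the trial. Allocation is by individual patient, so arm and centre are independent by design, and the ordinary standard error already covers chance imbalance. That stands. A reader might infer that treatment is likely to be confounded with centre. The documents do not support this, and step 3 shows neither bias nor an inflated error rate.

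A reader might also infer that usual care differs between centres. The plan leaves instructions to the local teams, so differences are possible, but it reports none. Nor does it say that the blocks are unstratified. It is silent, and the point is that the matter is unspecified.

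Section 3.4 does allow adjustment for imbalance, so it would be too strong to say that the analysis excludes centre. But that clause acts after the data are seen, does not name centre, and cannot recover the balance that stratification would have given.

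Two further objections stand in part. The sentence on delivery concerns arm A only, and Table I gives the arm B brochure to the recruiter alone. That is a difference between arms within a centre, and stratifying does not remove it. Separate local lists are also easier to predict. In a known block of 4 the last assignment is always determined and the third is determined with probability 1/3, so (1 + 1/3)/4 = 33% of assignments are known in advance. The recruiter enrols patients, can deliver either arm's materials and is not among those masked in section 3.3. Any fix must deal with this.

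**Conclusion.** The point holds as a missing specification with a modest cost to precision, not as a threat to validity. Marked imbalance in at least one municipality is more likely than not under equal sizes (8:4 or worse in about 71% of trials), and small municipalities make extreme splits more likely still.

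Whether power suffers depends on a variance share that the documents do not give. The gain from stratifying and adjusting is negligible if municipality hardly matters, up to about 3 points at 5 to 10%, and 4 to 6 points at 20%. The loss if municipality explains nothing is at most about 1 point. All power figures rest on the assumed 0.83 SD effect, 1:1 allocation and random municipality effects. The imbalance figures rest on the assumed municipality sizes. Since the gain outweighs the loss over the range considered and no patients are added, the change is worth making.

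**What to change.** In section 2.3.2, state that permuted blocks are generated separately within each of the four municipalities, with block sizes that vary at random and are not disclosed to the recruiter. Stratify by municipality rather than by CESFAM. The number of CESFAM is not stated, and many small strata would end in incomplete blocks.

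In section 3.4, prespecify municipality as a fixed factor in the ACT model. Compare adherence with a test stratified by municipality (Cochran-Mantel-Haenszel, in its exact form if the cells are sparse). A binary regression with three municipality terms may not be stable with 48 patients.

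The cost is four lists instead of one, 3 degrees of freedom, and somewhat more predictable local lists, which varied and undisclosed block sizes limit. Stratification has to be in place before the first patient, because it cannot be recovered for patients already assigned. The difference between arms in who delivers the materials remains and needs separate attention.
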